9.3.2. Statistical analysis of total lesion count

Total lesion count will be summarized for each treatment group and at each visit using mean, standard deviation, median, minimum, and maximum. The comparison between the two treatments will be based on the difference for each subject between each visit and Visit 2.

In accordance with ICH E9 guideline on Statistical Consideration in the Design of Clinical Trials (1998), the type 1 error rate of the test will be 5%.

At each post-baseline visit, an analysis of covariance (ANCOVA) will be performed to test the null hypothesis of no treatment effect. The dependent variable will be the difference between the value at each post-baseline visit, including endpoint, and the baseline value. The change from baseline to the endpoint (Visit 6) will be the primary efficacy analysis. The baseline value will be the covariate. Treatment group and study center will be the main effects in the model. This analysis will be performed on the MITT and PP populations. Efficacy will be declared if the treatment effect p-value for the MITT population is no greater than 0.05 and is favorable to ACU-D1 Ointment [REDACTED].

A second ANCOVA, which includes a treatment-by-center interaction, will be performed in order to test the significance of the interaction term in an exploratory manner. If the interaction term is significant at the 0.10 level, summary data will be presented for each study center in an appendix to the study report. In addition, if the interaction term is significant at the 0.10 level, the interaction term may be included in the final ANCOVA model to examine treatment effects if inclusion of this term increases the sensitivity of the analysis.

The residuals from the primary ANCOVA model will be analyzed for deviations from normality. If the test for normality fails at the 0.05 level of significance then the ANCOVA analysis will be supplemented by a Van Elteren test, stratified by study center.

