## **4. STUDY POPULATION**

Approximately 36 subjects, male and female, 18 years of age or older who meet all the inclusion criteria and none of the exclusion criteria will be enrolled at two United States investigational centers. Subjects will be randomized in a 2:1 ratio with 24 subjects randomized to treatment with ACU-D1 Ointment [REDACTED] and 12 subjects randomized to treatment with ACU-D1 Ointment Vehicle.

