### **8.1. Missing Values and Imputation**

For both MITT and PP analyses, the last non-missing observation (post randomization) of these subjects will be carried forward to any subsequent missing visits and to endpoints.

For analysis purposes, the endpoint analysis will use the last non-missing post-baseline data for each efficacy variable.

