### **8.11. Efficacy Analyses**

#### **8.11.1. Primary Efficacy Variables: Lesion Count**

Total lesion count will be summarized for each treatment group and at each visit using mean, standard deviation, median, minimum, and maximum. The comparison between the two treatments will be based on the difference for each subject between each visit and Visit 2.

In accordance with ICH E9 guideline on Statistical Consideration in the Design of Clinical Trials (1998), the type 1 error rate of the test will be 5%.

Proc Mixed in SAS will be used to develop a repeated measures analysis of covariance (ANCOVA) model to test the null hypothesis of no treatment effect. The dependent variable will be the difference between the value at each post-baseline visit, including endpoint, and the baseline value. The change from baseline to the endpoint (Visit 6) will be the primary efficacy endpoint. The baseline value will be the covariate. Treatment group and study center will be the main effects in the model. The mixed model will employ LOCF procedures for missing values. Efficacy will be declared if the treatment effect p-value for the MITT population is no greater than 0.05 and is favorable to ACU-DI Ointment [REDACTED]

A second ANCOVA, which includes a treatment-by-center interaction, will be performed in order to test the significance of the interaction term in an exploratory manner. If the interaction term is significant at the 0.10 level, summary data will be presented for each study center in an appendix to the study report. In addition, if the interaction term is significant at the 0.10 level, the interaction term may be included in the final ANCOVA model to examine treatment effects if inclusion of this term increases the sensitivity of the analysis.

The residuals from the primary ANCOVA model will be analyzed for deviations from normality. If the test for normality fails at the 0.05 level of significance then the ANCOVA analysis will be supplemented by a Van Elteren test using Proc Npar1way in SAS, stratified by study center. Subgroup analyses including but not limited to race, age and gender will be performed for exploratory purposes, provided adequate sample sizes are available in potential subgroups. Subgroups will be analyzed by adding the subgroup as a main effect and the interaction term of subgroup\*treatment to the model.

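### As worded, SAP 8.11.1 can put endpoint into the repeated-measures model as a duplicate row, and its primary p-value tests an effect pooled over rows, not the Visit 6 effect

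*SAP*

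**What the plan says.** Protocol 9.3.2 plans one analysis per visit: "At each post-baseline visit, an analysis of covariance (ANCOVA) will be performed to test the null hypothesis of no treatment effect". Endpoint is there one more stand-alone analysis with one row per subject. A repeated-measures model is only an optional exploratory addition.

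SAP 8.11.1 changes the primary model: "Proc Mixed in SAS will be used to develop a repeated measures analysis of covariance (ANCOVA) model". The response sentence is carried over from the protocol: "The dependent variable will be the difference between the value at each post-baseline visit, including endpoint, and the baseline value". The next sentence reads "The change from baseline to the endpoint (Visit 6) will be the primary efficacy endpoint". The model has baseline as covariate, with treatment group and study center as main effects. Missing values are filled by LOCF. Efficacy is declared if the treatment-effect p-value in the MITT population is at most 0.05. No covariance structure is named, and no visit or treatment-by-visit term is listed.

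Elsewhere the SAP uses *endpoint* in two ways:

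- **Separate from the visits.** SAP 8.1 says that "the endpoint analysis will use the last non-missing post-baseline data for each efficacy variable" and that the last value "will be carried forward to any subsequent missing visits and to endpoints". SAP 8.11.3 defines responders at the visits and, in addition, at endpoint.
- **One of the visits.** SAP 8.11.1 ties endpoint to Visit 6, and 8.11.2 and 8.11.3 also speak of an endpoint visit.

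Visit 7 (Day 99, after the no-treatment period) is also a post-baseline visit under SAP 6.

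**The concern.** With one ANCOVA per visit, an additional endpoint analysis overlaps with the Visit 6 analysis and does no harm. In a single repeated-measures model, the same phrase can be read as a list of response rows, with endpoint as one of them. After LOCF that row would equal another row for every subject, so it would carry no new information.

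Two programmers could each follow the SAP faithfully and build different datasets for the analysis that alone declares efficacy. At stake are whether an unstructured model can be fitted at all, how much weight each visit gets, and whether the deciding p-value answers the Visit 6 question that the SAP names as primary.

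**Working it through.** There is no planned figure to reproduce: Protocol 9.7 gives no power calculation, effect size or SD.

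**Inputs from the documents.** 24 active and 12 vehicle subjects, N = 36 (SAP 4); post-baseline Visits 3 to 7 (SAP 6); LOCF, so every row is filled; treatment, center and baseline in the model; type I error 5% (SAP 8.11.1; sidedness not stated, two-sided used here).

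**Assumed.** SD 8; within-subject correlation 0.3 to 0.7 for the weights and 0.5 or 0.7 for type I error; dropout 0% or 15%.

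**1. Rows.** Five visits give 36 × 5 = 180 rows. With an endpoint row there would be 36 × 6 = 216, of which 36 are copies. LOCF alone repeats values only for subjects with missing visits; an endpoint row repeats one for everybody.

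**2. Rank of the residual covariance matrix**, adjusted for treatment, center and baseline, in simulated data:

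| Response rows | Dimension | Rank |
|---|---|---|
| Visits 3–7 | 5 | 5 |
| Visits 3–7 + endpoint = Visit 6 | 6 | 5 |
| Visits 3–7 + endpoint = Visit 7 | 6 | 5 |
| Visits 3–6 | 4 | 4 |
| Visits 3–6 + endpoint = Visit 6 | 5 | 4 |

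**3. Unstructured likelihood with the copy.** Let e be the extra variance that separates endpoint from Visit 6. As e takes the values 1, 10⁻², 10⁻⁴ and 10⁻⁸, −2 log L is 826, 661, 495 and 163. Each hundredfold cut in e lowers it by 36 × ln(100) = 165.8, without limit, so there is no finite optimum.

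**4. Weight of Visit 6 in a treatment main effect.** With filled rows and working correlation R over m rows, the row weights are w = R⁻¹1 / (1′R⁻¹1).

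- *Compound symmetry* gives equal weights. Visits 3–7: 1/5 = 20% becomes 2/6 = 33%. Visits 3–6: 1/4 = 25% becomes 2/5 = 40%.
- *AR(1)* with correlation ρ gives an end row 1/(m − (m−2)ρ) and an inner row (1−ρ)/(m − (m−2)ρ). With the endpoint row placed last and ρ from 0.3 to 0.7, Visits 3–7 go from (1−ρ)/(5−3ρ) = 17% to 10% without the copy to (2−ρ)/(6−4ρ) = 35% to 41% with it. Visits 3–6 go from 1/(4−2ρ) = 29% to 39% to (2−ρ)/(5−3ρ) = 41% to 45%.

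**5. What the pooled effect estimates.** Take illustrative effects of −1, −2, −4, −6 and −4 at Visits 3 to 7, with equal weights:

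- no endpoint row: −17/5 = −3.4
- endpoint copies Visit 6: −23/6 = −3.8
- endpoint copies Visit 7: −21/6 = −3.5
- Visit 6 itself: −6

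Most of the gap to −6 comes from pooling, not from the copy.

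**6. Type I error under compound symmetry.** On filled data the main-effect test equals an ANCOVA of each subject's row mean. In 10,000 runs per setting (Monte Carlo standard error about √(0.05 × 0.95/10,000) = 0.2 percentage points), it was 4.7% to 5.4% without the copy and 4.8% to 5.4% with it.

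**7. Normality trigger.** Shapiro-Wilk on pooled residuals of exactly normal data (3,000 runs; ranges over variants of the simulation) rejected as follows:

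| Correlation | Without copy | With copy |
|---|---|---|
| 0 | 5% | 14–15% |
| 0.5 | 7–10% | 20–21% |
| 0.7 | 17–20% | 31–34% |

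At correlations 0.5 and 0.7, part of the excess over 5% is there without any copy, because correlated residuals are pooled.

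**The case against.** A reader might infer that the SAP definitely adds a sixth row and that its primary model therefore cannot be fitted. The documents support neither statement without conditions. The label *endpoint (Visit 6)* and the term *endpoint visit* fit a reading in which Visit 6 is simply one of the listed visits and no row is added. Nor does the SAP ask for an unstructured covariance: compound symmetry or AR(1) would run with the copy, and a singular fit would be noticed before any result was read.

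A reader might also infer a raised false-positive rate. Under compound symmetry there was none. The check did not cover the AR(1) test.

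The normality trigger is also a small matter, because the Van Elteren test only supplements the ANCOVA and the declaration of efficacy stays with the model's p-value. In the illustration, double-counting Visit 6 even moves the pooled effect towards the Visit 6 value.

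These points stand and limit the claim. They do not remove the ambiguity, since SAP 8.1 and 8.11.3 treat endpoint as something beside the visits. They also leave the pooling untouched: with the terms listed, deleting the extra row would still leave no Visit 6 contrast to test.

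**Conclusion.** The concern holds as an ambiguity with a definite consequence. Wording that was harmless in by-visit ANCOVAs now sits in one repeated-measures model, where a literal build adds a row that duplicates Visit 6, or Visit 7 on the wording of SAP 8.1.

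If that row is added, an unstructured covariance is singular, and under compound symmetry Visit 6 carries 33% instead of 20% of the pooled effect (40% instead of 25% with Visits 3–6 only). The weights and the rank do not depend on the assumed SD; the AR(1) weights depend on the assumed correlation. The effects in step 5 are illustrative only.

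The more important point does not depend on the extra row. With no visit or treatment-by-visit term listed, the p-value that declares efficacy refers to an effect pooled over rows, although the SAP names the Visit 6 change as the primary endpoint. This should be settled before unblinding. It is not evidence of an inflated error rate or of a model that must fail.

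**What to change.** In SAP 8.11.1:

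1. Delete the words *including endpoint* from the response sentence. State which visits are in the model, that each subject contributes one row per scheduled post-baseline visit, and that endpoint is the Visit 6 row and not an additional level.
2. Add visit and treatment-by-visit terms.
3. Name the covariance structure.
4. Base the declaration of efficacy on the Visit 6 treatment contrast.

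Keep a separate endpoint value only for analyses with one row per subject (responders, Van Elteren), and align SAP 8.1 so that its definition cannot be taken to mean Visit 7.

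**Cost.** No new data. With Visits 3–7, the two added terms use 4 + 4 = 8 fixed-effect parameters. An unstructured 5 × 5 covariance would have 5 × 6/2 = 15 parameters, against 2 for compound symmetry, which is a real consideration with 36 subjects. With the copy removed the unstructured matrix has full rank (5 of 5, or 4 of 4 for Visits 3–6), so the choice is open, but it must be fixed before unblinding.

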### **7.3. Subject Discontinuation**

Subjects will be informed that they are free to withdraw from the study at any time and for any reason. The investigator may remove a subject from the study if, in the investigator's opinion, it is not in the best interest of the subject to continue the study.

In case of premature discontinuation of study participation, efforts will be made to perform all the Visit 6 assessments for discontinuations during the treatment period and all the Visit 7 assessments for discontinuations during the no-treatment period.

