## **8.6. Subject Disposition**

Subject disposition summary will include the number and percentage of subjects in each of the following categories:

- Subjects completing the study
- Subjects withdrawn early from study
- Reasons for discontinuation from study

Percentages will be based on the number of subjects randomized.

Subject disposition will be presented in a listing.

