## **8.7. Study Visits**

The number and percentage of subjects at each scheduled visit will be tabulated. By-subject data listing for visit participation will be prepared.

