### **8.9. Extent of Exposure**

Extent of exposure will be defined as the total ordinal number of days a subject is exposed to any study treatment. This will be calculated for each subject by taking the difference between the visit at which the first administration of study treatment took place and the date of last application. For subjects who are lost to follow-up, extent of exposure will be calculated based on the last study visit attended.

A summary of the number of days of exposure will be prepared for subjects in the Safety population.

The data for extent of exposure will be presented in a listing.

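### The primary mixed model is fitted to LOCF-filled lesion counts, and the SAP pre-specifies no analysis of the primary endpoint without LOCF

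*SAP*

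**What the plan says.** SAP 8.11.1 specifies a PROC MIXED repeated-measures ANCOVA of change from baseline, with this rule for gaps: "The mixed model will employ LOCF procedures for missing values". SAP 8.1 sets the same rule for the MITT and PP analyses: the last post-randomization value "will be carried forward to any subsequent missing visits and to endpoints".

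The time point is named: "The change from baseline to the endpoint (Visit 6) will be the primary efficacy endpoint". The terms are a baseline covariate plus two factors: "Treatment group and study center will be the main effects in the model". No visit or treatment-by-visit term is listed. Efficacy is declared if the MITT p-value is at most 0.05 and favors active.

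Protocol 9.2.1 and 9.2.2 also prescribe LOCF. Protocol 9.3.2 mentions a mixed-model analysis across visits, but it is optional and exploratory.

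**The concern.** A likelihood-based repeated-measures model on the observed visits is valid when data are missing at random. It uses each leaver's earlier counts, with the correlation between visits, to inform the Visit 6 comparison. Filling the gaps first gives that up. A carried count is treated as a measurement at a visit the subject did not attend, and the model is told that the lesion count stopped changing when the subject left.

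In a 12-week trial where counts are expected to fall, an early leaver's carried value will usually understate the improvement the subject would have shown at Day 85 by staying. If leaving differs between arms in frequency or timing, that understatement does not cancel. It goes straight into the treatment effect on which efficacy is declared. With 12 vehicle subjects and no replacement (Protocol 4.8), three leavers are already 25% of that arm.

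**Working it through.** **1. Is there an analysis without LOCF?** For the primary variable the SAP plans the main model (MITT), the PP analysis, a model with a treatment-by-center interaction, a Van Elteren test if normality fails, and subgroup models. None names another missing-data rule, so SAP 8.1 governs all of them. The protocol's exploratory mixed model is not carried into the SAP and is not said to omit LOCF.

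**2. Inputs.** From the documents: 24 active and 12 vehicle; visits 14, 28, 56 and 84 days after Visit 2; two centers (SAP 4 and 6). Assumed, because Protocol 9.7 reports no prior data: SD of the change 8, within-subject correlation 0.6, dropout at random within arm and spread evenly over last visits 3, 4 and 5, linear improvement *m* by day 84. There is no plan figure to reproduce.

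**3. Formula.** If a share *p* of an arm leaves with a last count on day *d*, the mean Visit 6 improvement after LOCF is *m*(1 − *p*) + *m*(*d*/84)*p*. Hence

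bias toward active = *p*V × *m*V × (1 − *d*/84) − *p*A × *m*A × (1 − *d*/84).

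Equal improvement of 10, no true effect:
- 5% active, 25% vehicle: 10 × 0.20 × (1 − *d*/84) = 1.67, 1.33, 0.67 for *d* = 14, 28, 56; mean 1.22.
- 10%, 15%: 0.42, 0.33, 0.17; mean 0.31.
- 20%, 5%: −1.25, −1.00, −0.50; mean −0.92.

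Unequal improvement, 15 active and 10 vehicle (true difference 5), dropout 15% and 20%: 4.79, 4.83, 4.92. More vehicle than active subjects leave, yet the estimate falls, because active leavers had more improvement still to come.

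**4. Simulation under no effect.** 20,000 trials per row, Visit 6 ANCOVA on LOCF data with baseline, center and treatment:

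| Dropout, active / vehicle | False benefit (lesions) | Favorable rejection (nominal 2.5%) | Two-sided |
|---|---|---|---|
| 0 / 0 | 0.01 | 2.3% | 4.8% |
| 15% / 15% | 0.01 | 2.7% | 5.4% |
| 10% / 15% | 0.27 | 3.0% | 5.0% |
| 10% / 20% | 0.57 | 3.9% | 5.6% |
| 5% / 25% | 1.23 | 6.4% | 7.4% |
| 20% / 5% | −0.93 | 1.1% | 5.7% |

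The standard error at 5% / 25% is 2.93, so the shift there is 1.23/2.93 = 0.42 of a standard error. A repeat of that row gave 1.21 lesions and 5.9% favorable rejection.

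**5. Other readings and shapes.** With only the listed terms, the treatment effect is an average over Visits 3 to 6. The shift is then smaller: 0.50 and 4.1% favorable at 5% / 25%; 0.22 and 3.1% at 10% / 20%; 0.09 and 2.7% at 10% / 15%. That average is not a Visit 6 contrast: with complete data and improvements of 15 and 10 it equals 5 × (14 + 28 + 56 + 84)/(4 × 84) = 2.71, not 5. An earlier plateau also shrinks the Visit 6 shift at 5% / 25%: 0.83 and 5.0% if improvement stops at day 56; 0.32 and 3.2% if it stops at day 28.

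**6. With a true effect.** A second set of assumptions uses improvement at Visits 3 to 6 of 6/11/14/16 on active and 4/7/9/10 on vehicle (true difference 6), with all leaving after Visit 3. LOCF expects 6 − (4/24)(10) + (2/12)(6) = 5.33 with 4/24 and 2/12 leaving; 3.50 with 6/24 and 0/12; 7.17 with 2/24 and 4/12. Simulated LOCF rejection was 37%, 15% and 63% respectively, against 52% with no dropout.

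**7. Without LOCF.** An observed-data REML model (visit-specific treatment effects, unstructured covariance, 4,000 trials) at 5% / 25% gave −0.09 lesions (Monte Carlo standard error about 0.05), 2.4% favorable and 5.1% two-sided, with a standard error of 3.02.

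**The case against.** **Estimand.** Protocol 9.2.1 and SAP 8.1 define the endpoint value as the last available count, so LOCF could be called the definition rather than a distortion. This stands in part: the bias figures measure distance from the result had leavers stayed. But SAP 8.11.1 fixes the endpoint at Visit 6, and a carried Day 15 count is not a Visit 6 count.

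**Exit assessments.** SAP 7.3 says "efforts will be made to perform all the Visit 6 assessments for discontinuations during the treatment period". If leaving were uniform over 84 days and every exit count obtained, the 5% / 25% shift would be 10 × 0.5 × 0.20 = 1.00 rather than 1.22. The carried count sits nearer to departure, but it is still not a Day 85 count.

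**Visibility.** The disposition table includes "Subjects withdrawn early from study"; attendance is covered ("The number and percentage of subjects at each scheduled visit will be tabulated"), and so is exposure ("A summary of the number of days of exposure will be prepared for subjects in the Safety population"). With the listings, 36 subjects could be re-analyzed. These outputs would expose unequal leaving, but a re-analysis chosen after unblinding is not pre-specified.

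**Size.** The 5% / 25% case is unfavorable, about 1 of 24 against 3 of 12, and assumes linear improvement. With a 4/7/9/10 trajectory it falls to 0.65 lesions and 4.1% favorable; at 10% / 15% it is 0.14 and 2.8%. This stands and limits the severity.

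**Pilot status.** It lowers the stakes, but the SAP still declares efficacy from this p-value.

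**Conclusion.** The concern holds. The primary model is fitted to LOCF-filled data, and no planned SAP analysis of the primary endpoint does without it. The resulting shift depends on the arm and timing of dropout and can favor or penalize active. It is zero with no dropout, or with equal dropout, equal timing and no treatment effect.

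In the no-effect scenarios it runs from 0.09 lesions (10% / 15%, averaged over visits) to 1.23 lesions (5% / 25%, Visit 6) when vehicle dropout is higher, and is −0.93 at 20% / 5%. It stays below the standard error, so it shifts the result rather than deciding it. In the most unequal case it still more than doubles the nominal favorable error rate. All sizes rest on assumed trajectories, SD, correlation and dropout. The plan should be changed, but this flaw alone would not invalidate the trial.

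**What to change.** In SAP 8.11.1, replace the LOCF sentence with a likelihood-based repeated-measures model fitted to observed changes at Visits 3 to 6. Its terms should be baseline, center, treatment, visit and treatment-by-visit, with a stated covariance structure (for example unstructured) and a named fallback. The primary test is the treatment contrast at Visit 6. Deleting the LOCF sentence alone is not enough, since the listed terms give no Visit 6 contrast. Drop the separate endpoint record from the repeated measures, and assign early-termination counts by actual study day. Align SAP 8.1 and Protocol 9.2.1 and 9.2.2, and keep LOCF as a named sensitivity analysis.

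At minimum, if LOCF stays primary, add this observed-data model as a pre-specified sensitivity analysis.

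The full change costs SAP wording and programming before unblinding, plus a protocol amendment, which needs IRB approval under Protocol 11.1. No new visits or data are needed. The standard error rises somewhat when visits are missing: 2.93 to 3.02, about 3%, at 5% / 25%. The new model estimates the result as if leavers had stayed and rests on missing-at-random, which cannot be tested. The minimum option costs one extra table.

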9.7. Sample Size Determination

This is a pilot study for which no previous data are available to make a power calculation. This will be the seminal study.

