## **6. TRIAL DESIGN**

This is a randomized, double-blind, vehicle-controlled, parallel-group study of ACU-D1 Ointment [REDACTED] and the ACU-D1 Ointment Vehicle in subjects with papulopustular rosacea on the face.

Subjects will be randomized in a 2:1 ratio with 24 subjects randomized to treatment with ACU-D1 Ointment [REDACTED] and 12 subjects randomized to treatment with ACU-D1 Ointment Vehicle

The study will be conducted at two United States investigational centers.

Study visits are:

- Visit 1 (Day -13 to 0) enrollment and start of the screening period
- Visit 2 (Day 1) randomization and start of the study medication treatment period

Accutis, Inc.

Protocol number: ACU-D1-201

- Visit 3 (Day 15) treatment period follow-up
- Visit 4 (Day 29) treatment period follow-up
- Visit 5 (Day 57) treatment period follow-up
- Visit 6 (Day 85) end of the treatment period and start of the no treatment follow-up period
- Visit 7 (Day 99) no treatment follow-up, end of study.

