**8.11.4. Secondary Efficacy Variable: Individual lesion counts**

As ancillary efficacy parameters, papules, pustule, and nodule counts will be summarized for each treatment group and at each visit using mean, standard deviation, median, minimum, and maximum. Change from baseline for papule, pustule, nodule, and papule plus pustule counts will be analyzed at each post randomization visit using the same parametric or non-parametric analysis as was used in the primary efficacy variable (total inflammatory lesions).

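### The fallback rank test for lesion counts omits the baseline adjustment used in the primary ANCOVA, so it can lose power and differ from the ANCOVA in two respects at once

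*SAP*

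**What the plan says.** SAP 8.11.1 and Protocol 9.3.2 both analyze change in total lesion count with the baseline count as covariate and treatment and center as main effects. Both then test the residuals for normality at the 0.05 level. On failure, the SAP says "then the ANCOVA analysis will be supplemented by a Van Elteren test using Proc Npar1way in SAS, stratified by study center" and the Protocol says "then the ANCOVA analysis will be supplemented by a Van Elteren test, stratified by study center". Neither gives this test a baseline term or a baseline stratum.

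The sentence does not name the response to be ranked. The same SAP section states that "The comparison between the two treatments will be based on the difference for each subject between each visit and Visit 2", so raw change from Visit 2 is the natural reading.

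SAP 8.11.4 has the papule, pustule, nodule and papule-plus-pustule counts analyzed "using the same parametric or non-parametric analysis as was used in the primary efficacy variable", so the choice carries over to them. Efficacy is declared on the treatment p-value from the primary model in the MITT population. The Van Elteren test has no part in that rule, and neither document says how a disagreement between the two tests is to be read.

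**The concern.** A robustness check is easiest to read when it changes one thing. This one relaxes the normality assumption and, in the same step, removes the covariate adjustment.

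The adjustment may matter here. Protocol 4.3 admits subjects with 10 to 40 lesions. Someone who starts at 10 can lose at most 10; someone who starts at 40 can lose 40. If half the lesions clear, the changes are -5 and -20 for the same proportional response. A rank test on raw change treats that spread as noise, while the ANCOVA removes most of it.

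At stake is how the supportive analysis reads in a trial of about 36 subjects, and how sensitive the individual lesion count analyses are. A non-significant fallback beside a significant ANCOVA might reflect non-normality, the cost of ranking or the missing covariate, and the reader could not tell which.

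**Working it through.** **Inputs from the documents.** Allocation is 24 to 12 (SAP 4). There are two centers (SAP 6: "The study will be conducted at two United States investigational centers"). The type I error rate is 5% (SAP 8.11.1), taken here as two-sided because sidedness is not stated. Entry counts are 10 to 40. No effect size, SD or power is given (Protocol 9.7: "This is a pilot study for which no previous data are available to make a power calculation"), so there is no planned figure to reproduce and everything below rests on assumptions.

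**Analytic check.** Let b be the slope of follow-up on baseline, s_e the residual SD and s_B the baseline SD. Adjusted variance is s_e². Unadjusted variance of change is s_e² + (1-b)² s_B². With s_e = 7 and s_B = 7.5 (before truncation to 10-40, so slightly too large), the adjusted-to-unadjusted ratio is:
- b = 0.3: 49 / (49 + 0.49 × 56.25) = 49 / 76.56 = 0.64
- b = 0.5: 49 / (49 + 0.25 × 56.25) = 49 / 63.06 = 0.78
- b = 0.8: 49 / (49 + 0.04 × 56.25) = 49 / 51.25 = 0.96
- b = 1.0: 49 / 49 = 1.00

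With equal SDs at baseline and follow-up and correlation rho, the ratio reduces to (1 + rho)/2: 0.65, 0.75, 0.85 and 0.95 at rho = 0.3, 0.5, 0.7 and 0.9. The penalty is real at low slopes and vanishes at slope 1.

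**Simulation.** 4,000 trials per scenario, two centers of 18 (12:6 in each), baseline 10-40. Three tests were compared: single-visit ANCOVA on change with baseline, center and arm; Van Elteren on raw change by center; and Van Elteren on the residuals from regressing within-center ranked change on ranked baseline. The normal scenarios use baseline mean 20, SD 7.5, residual SD 7 and an effect of 7 lesions. The skewed scenarios use negative binomial follow-up proportional to baseline, with active 45% below vehicle. As a calibration check, an effect of 1 SD with 12 and 24 subjects has 80.7% power by the two-sample formula, close to the 77-78% found for ANCOVA in the normal cases.

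Power (%):

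| Scenario | ANCOVA | Van Elteren, raw change | Rank test with baseline | Gain from baseline (points) |
|---|---|---|---|---|
| Normal, slope 0.3 | 77.7 | 61.5 | 69.4 | +7.9 |
| Normal, slope 0.5 | 78.2 | 67.4 | 71.2 | +3.8 |
| Normal, slope 0.8 | 78.2 | 74.3 | 73.3 | -1.0 |
| Normal, slope 1.0 | 76.6 | 75.4 | 73.6 | -1.8 |
| Skewed, vehicle fraction 0.4, dispersion 3 | 63.1 | 31.4 | 46.1 | +14.7 |
| Skewed, 0.6, dispersion 3 | 66.0 | 46.3 | 51.8 | +5.5 |
| Skewed, 0.6, dispersion 1.5 | 45.5 | 30.9 | 32.1 | +1.2 |
| Skewed, 0.8, dispersion 3 | 69.7 | 56.2 | 57.1 | +0.9 |

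The simulation standard error of one power figure is at most √(0.25/4000) = 0.8 points, so gains or losses of about one point are not distinguishable from zero. With no effect, all three tests rejected in 4.4 to 5.3% of trials.

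**Disagreement with the ANCOVA at 0.05, with an effect present.** Without and then with baseline in the rank test:
- Normal: 22.7 to 13.5%, 16.4 to 11.5%, 9.9 to 8.9%, 8.4 to 8.6% (slopes 0.3 to 1.0)
- Skewed, in table order: 38.4 to 23.3%, 27.1 to 20.2%, 22.2 to 20.5%, 21.1 to 17.7%

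The part due to the missing baseline is therefore about 0 to 9 points (normal) and 2 to 15 points (skewed). With no effect, the planned test disagreed with the ANCOVA in only 3 to 6% of trials.

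**Allowing for the trigger.** Shapiro-Wilk (assumed, since no test is named) failed in about 5% of normal trials and 47 to 71% of skewed ones. A separate run used multiplicative reduction with active/vehicle ratios to baseline of 0.40/0.65, 0.35/0.60 and 0.40/0.70 and log-SDs of 0.5, 0.4 and 0.6. Power for ANCOVA / Van Elteren / rank ANCOVA was 61/50/56%, 83/65/75% and 60/51/55%, so baseline gained 6, 10 and 4 points. Among ANCOVA-positive trials, Van Elteren was non-significant in 24-26% (rank ANCOVA 12-17%). Counting only trials in which the normality test had also failed, this was 10-16% (rank ANCOVA 4-11%).

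**The case against.** The strongest reply is that no decision depends on this test. It is prespecified, it holds its type I error, and it only accompanies an ANCOVA that alone decides efficacy, in a pilot with no power calculation. That stands: it confines the point to interpretation and to the individual lesion counts, which the SAP calls ancillary.

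Three further objections also stand in part:
- Baseline is not ignored, because it is subtracted in the change score. What is lost is the covariate adjustment, and the loss depends on a slope the documents do not give. Near slope 1 the planned test is no worse, and may be slightly better.
- Ranking has its own cost. The baseline-adjusted rank test was still 3 to 8 points below ANCOVA in the normal cases and about 13 to 17 below in the skewed ones. In every scenario more than half of the disagreement remained after adjustment.
- The comparator was a single-visit ANCOVA, as in Protocol 9.3.2. SAP 8.11.1 specifies a repeated-measures model with LOCF, which was not simulated. Any single-visit rank test would differ from that model in more than distribution, so the fix narrows the mismatch without removing it.

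A reader might infer that the fallback will often contradict a sound positive ANCOVA for reasons unrelated to non-normality. The plan does not support this: the test runs only when normality fails, much of the disagreement is the price of ranking, and the share due to baseline is sizeable only when change is strongly related to baseline.

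**Conclusion.** The point holds in a limited form. The fallback omits the adjustment the primary model makes. If change depends on the starting count, it therefore loses power and can disagree with the ANCOVA partly for that reason. Adding baseline is worth about 1 to 15 power points in the skewed-count scenarios and about -2 to +8 in the normal ones, with no gain near slope 1. These figures assume the effect sizes, spreads, baseline shape, equal centers and normality test listed above.

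The effect falls on the robustness check and on the individual lesion counts. A reader might also infer that a positive trial could be overturned or that the error rate is inflated. Neither follows, since the efficacy rule uses only the primary-model p-value and the planned test rejected at about 5% under no effect.

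**What to change.** In SAP 8.11.1 and Protocol 9.3.2:
1. Name the response for the rank analysis as change from Visit 2 to Visit 6/endpoint.
2. Replace the Van Elteren test with a center-stratified rank ANCOVA. Within each center, rank the change and the Visit 2 count, regress the first on the second, and compare the residuals between arms with the center-stratified extended Mantel-Haenszel mean-score test (PROC RANK, REG, then FREQ with CMH2).
3. State that the result is supportive and does not override the primary model, and how a disagreement will be reported.

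SAP 8.11.4 then follows by its own cross-reference, with the Visit 2 count of the same lesion type as covariate. The IGA sections (SAP 8.11.2 and Protocol 9.4.1) also refer back to the Van Elteren test as defined for the primary variable, so that definition should be moved there and not simply deleted.

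The cost is an amendment to the text before unblinding and a few lines of code, with no new data. The downsides are a little more explanation in the report and a small power loss (up to about 2 points here) if change turns out to be unrelated to baseline.
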